Data sampling/extraction criteria:	Patients are sampled if they have a confirmed diagnosis of metastatic breast cancer via abstraction on or after 1 Jan 2011, and at least 2 EHR visits on or after 1 Jan 2011. Both ICD-9 (174.x) and ICD-10 (C50.x) codes are used for the initial selection, and advanced diagnosis are then confirmed via abstraction (since ICD codes do not specify advanced diseases).	This database identifies patients for curation using a structured ICD-10 diagnosis code (ICD-10 C50*), corresponding to the indication of interest, along with at least the year of diagnosis. Once this initial screening list is generated, patients are randomly selected for further review. Curation begins with confirmation of the diagnosis and diagnosis date, primarily based on pathology reports and other unstructured data sources. All patients must be over 18 years of age at the time of their first diagnosis. Certain breast cancer cases are excluded from curation. Specifically, in-situ breast cancers such as ductal carcinoma in situ (DCIS) or lobular carcinoma in situ (LCIS) without an invasive component are not eligible. However, DCIS with microinvasion or DCIS associated with Paget's disease qualifies for curation. Additionally, in-situ breast cancers that later progress to invasive carcinoma are eligible; in	Breast cancer patients with an office visit in the reporting period will be included in the report with full patient history. Patients are sampled if they were diagnosed with breast cancer and with a documented visit date, within the defined reporting period, to one of the facilities and were at least 20 years of age at the time of first diagnosis. Patients who were on a clinical trial at any point in their treatment history are excluded.

		
these cases, the diagnosis date should reflect the date of the original in-situ diagnosis, not the later invasive diagnosis.
 
Patients are ultimately selected for inclusion in data products through quality control processes that assess consistency and potential conflicts in their records. These evaluations may rely on structured data alone or a combination of structured and curated data, depending on the specific data product. Importantly, CAI does not exclude patients based on data completeness, in order to prevent the introduction of selection bias.
	
Type(s) of data:	EHR-derived	EHR-derived	EHR-derived

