- **EDB4:** Time in [days, months and years] from index date to death due to any reason. The date of death is de-identified to month-level granularity and the day of death is therefore imputed to the 15th of a month. If there is no indication that a patient died during the study period, the patient is censored. The censoring date is defined as the last date of vital signs recorded as proof that the patient was alive at that time (de-identified to week-level granularity) or data cut-off date, whichever occurred earlier. The OS endpoint is operationalized using a parameterized R function *edb4_get_os()* and more details can be found in the attached pdf documentation.

Table 4. Relevant clinical activities considered to derive last activity date for censoring.

Table / clinical activity considered	Dates considered
Adverse events	Event date
Therapy (cellular, systemic, radiation, surgery)	Start and end dates or declined intervention date, surgery date, assessed resection dates
Palliative care referral	Referral date
Visits	Contact/visit date
Vitals	Assessed date
Labs	Lab date
Biomarkers	Specimen collection date
Patient observation period	Start and end dates

Demographics	Date of most recent contact with provider, date patient was diagnosed with a second primary malignancy
Performance assessments	Documented date, reported date
Secondary diagnoses	Diagnosis date
Progression, histology, lymphovascular invasion, metastatic sites, pancoast tumor, perineural invasion	Assessed date
Stage/TNM	Assessed date
Smoking	Assessed date

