Socio-economic status	dem_ses	edbx_get_demographics()	Socioeconomic status (SES) index based on residence area of patient. Not available in EDB3 and EDB4.	Nominal (from '1 - Lowest SES' through '5 - Highest SES')	[-inf;0]
Smoking	c_smoking_history	edbx_get_demographics()	History of current or former (= TRUE) or never (= FALSE) smoking on or anytime before index date; if there are multiple records per patient, any evidence of former/current smoking is prioritized. IN EDB1, "smoking history" is not available for breast cancer.	Binary logical (TRUE, FALSE)	[-inf;0]
ECOG	c_ecog	edbx_get_ecog()	ECOG performance status measured closest to index date within assessment window. In	Nominal (0, 1, 2, 3, 4); modelled as ordinal numeric in ROPRO ¹⁰ ; due to I/E	[-90;0]

Characteristic	Harmonized analysis variable name	R function to derive covariate (see pdf in appendix)	Details ¹	Variable encoding	Assessment window
			case of ties, the lower ECOG value is selected	criteria ECOG is modelled as a binary (0, 1) covariate	
Stage	c_stage_initial_dx	edbx_get_diagnosis_solid()	AJCC summary group stage at initial diagnosis	Ordinal numeric (from 0 to IV with sub-categories, e.g., IA1) ¹⁰	[-inf;0] at initial diagnosis of primary cancer
De novo metastatic status	c_de_novo_mets_dx	edbx_get_diagnosis_solid()	Evidence of presence of one or multiple metastases at/before initial diagnosis	Binary logical (TRUE, FALSE)	[-inf;0] at initial diagnosis of primary cancer
Number of metastatic sites	c_number_met_sites	edbx_get_diagnosis_solid()/edbx_get_number_met_sites_solid()	Number of metastatic sites for a given patient before/on index date	Integer	[-inf;X]; Proprietary business-rule-based covariate assessment window
Time between initial diagnosis to index date	c_time_dx_to_index	edbx_get_diagnosis_solid()	Time in days between initial diagnosis to index date. Quartiles will be used because there may be “negative” times intervals due to date imprecision of the lines of therapy.	Categorical (quartiles)	[-initial dx;0]
Time between earliest evidence of a metastatic and index date	c_time_met_dx_to_index_quartiles	edbx_get_diagnosis_solid()	Time in days between earliest evidence of a metastatic diagnosis and index date. Quartiles will be used because there may be “negative” times intervals due to date imprecision of the lines of therapy.	Categorical (quartiles)	[met dx;0]

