	
In subgroup analysis, multiple imputation, propensity score matching and balance assessment will be conducted within each subgroup separately. The treatment effect will be estimated for each stratum separately (stratum-specific effects).
 
 1. Age (<65, ≥65) 2. Region (North America, Europe, Asia/Pacific) 3. ECOG (0, 1) 4. Disease-free interval (De-novo metastatic, ≤12 months, >12 months) 
According to Slamon et al,⁶ the subgroup analyses are considered exploratory in nature and performed with no formal statistical testing.

Table 8. Sensitivity analyses – rationale, strengths and limitations.

	What is being varied? How?	Why? (What do you expect to learn?)	Strengths of the sensitivity analysis compared to the primary	Limitations of the sensitivity analysis compared to the primary
Sensitivity #1	Caliper matching on ROPRO prognostic score instead of propensity score	Matching patients on validated prognostic score may be more beneficial to control for (unmeasured) confounding	Matches patients on validated prognostic score that incorporates weights of key prognostic factors	Limited experience on how to optimally use prognostic scores and should be seen as an experimental sensitivity analysis
Sensitivity #2	Average treatment effect in the overlap population (ATO) weighting instead of matching	Weights that resemble the average treatment effect in the overlap population (ATO) create a clinical equipoise population which is comparable to an RCT	ATO weighting usually results in excellent balance and clinical equipoise	Estimates the average treatment effect among the overlap patients which may not be comparable to target population anymore
Sensitivity #3	SMR/ATT weighting instead of matching. Here symmetric trimming (i.e., setting all weights lower/higher than that at a given quantile to the weight at the quantile) of extreme weights may be considered with the quantiles chosen based on weight distribution and resulting balancing performance.	SMR weighting retains all patients and resembles the same estimand as matching	ATT weighting retains all patients	Patients with extreme weights after trimming may bias the analysis

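### EDB3 dates in-situ-first cancers at the in-situ lesion, and Table 5 carries that date into time since diagnosis and de novo status without an exception

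*Combined protocol and SAP*

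**What the plan says.** Table 3 in section 6.1.1 describes how EDB3 patients are selected for curation. Pure in-situ disease is excluded, but "Additionally, in-situ breast cancers that later progress to invasive carcinoma are eligible". For those cases "the diagnosis date should reflect the date of the original in-situ diagnosis, not the later invasive diagnosis". The table states no comparable rule for EDB1 or EDB4.

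Table 5 in section 6.6.7 derives three covariates from initial diagnosis through the same family of functions:

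- c_time_dx_to_index: "Time in days between initial diagnosis to index date", used in quartiles.
- c_de_novo_mets_dx: "Evidence of presence of one or multiple metastases at/before initial diagnosis".
- c_stage_initial_dx: "AJCC summary group stage at initial diagnosis", encoded as "Ordinal numeric (from 0 to IV with sub-categories, e.g., IA1"), so stage 0 is an allowed value.

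None of the three rows says what to do when the recorded initial diagnosis is in situ. Table 7 in section 6.7.1 lists a subgroup, "Disease-free interval (De-novo metastatic, ≤12 months, >12 months"), without saying which dates or variables define the interval. Neither section 7 nor the sensitivity analyses in Table 8 take up the point.

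**The concern.** Time since diagnosis and de novo status are meant to describe the course of the cancer being treated. For an in-situ-first woman in EDB3 they describe the time since a lesion that was not yet invasive. A woman whose first invasive cancer presents with metastases is then recorded as a late recurrence. If matching uses these fields, she can be paired with women who relapsed years after treatment for invasive disease. The balance plots would not show this, because they are drawn from the same fields.

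The subgroup is exposed more directly. Imputation, matching and estimation are repeated within each stratum, so a woman in the wrong stratum contributes to the wrong estimate. Sensitivity analysis #6 refers to the Table 7 subgroup factors when re-weighting to the trial population, so it could inherit the same error.

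**Working it through.** **Step 1. Apply the written rules to two illustrative women in EDB3, both treated in 2019.**

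Woman A: in-situ lesion in 2008; first invasive cancer found in 2019, already metastatic. Woman B: in-situ lesion in 2008; stage II invasive cancer in 2014; metastatic in 2019.

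| Field | A, as written | A, first invasive anchor | B, as written | B, first invasive anchor |
|---|---|---|---|---|
| Time to index | 2019 − 2008 = 11 years | about 0 | 11 years | 2019 − 2014 = 5 years |
| De novo | FALSE | TRUE | FALSE | FALSE |
| Stage | not determined: 0, or IV in conflict with the flag | IV | not determined: 0 or II | II |
| Disease-free interval, if built from these fields | >12 months | de novo | >12 months | >12 months |

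Time is wrong for both women. De novo status, and the subgroup if it uses these fields, is wrong only for A. Stage cannot be settled from the text, because the EDB3 rule fixes a date and not a stage.

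**Step 2. Reproduce the plan's EDB3 figure, to fix the scale.** Inputs from section 10.3: 331 events in EDB3, 1021 in EDB1, 610 matched women in EDB3, alpha 0.05, 50% exposed, HR 0.92. Schoenfeld power, two-sided, is Φ(√(d × 0.25) × |ln 0.92| − 1.96).

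- EDB3: √82.75 × 0.0834 − 1.96 = −1.20, power 0.115 (plan: 0.11).
- EDB1: √255.25 × 0.0834 − 1.96 = −0.63, power 0.265 (plan: 0.27).

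Both agree. The same approximation gives a standard error of the log HR of 2/√331 = 0.110 in EDB3 and 2/√1352 = 0.054 pooled. The fixed-effect weight of EDB3 is about 331/1352 = 24.5%.

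**Step 3. Size of the effect on the hazard ratio.** The documents give neither the share of in-situ-first women nor its split by arm, so both are assumed. Let f be the average share affected, f₁ and f₀ the shares in the two arms, and R the mortality ratio between the true and the recorded prognostic group (assumed 1.25 to 2.0). Approximate bias in the EDB3 log HR is ln[(f₁R + 1 − f₁)/(f₀R + 1 − f₀)]. Multiply by 0.245 for the pooled log HR.

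| Split by arm, f = 0.5% to 5% (about 3 to 31 of 610) | EDB3 log HR bias | In EDB3 SEs | Pooled HR multiplied by |
|---|---|---|---|
| Equal | about 0 | 0 | 1.000 |
| Threefold (1.5f against 0.5f) | 0.001 to 0.048 | 0.01 to 0.43 | 1.0003 to 1.012 |
| All in one arm (2f against 0) | 0.002 to 0.095 | 0.02 to 0.87 | 1.0006 to 1.024 |

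At f = 10% (61 women), R = 2.0 and all in one arm, the pooled factor is exp(0.245 × ln 1.2) = 1.046.

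A milder case is a 2-point difference between arms with R of 1.3 to 1.5. The EDB3 shift is then 0.02 × ln 1.3 = 0.005 to 0.02 × ln 1.5 = 0.008, at most 0.008/0.110 = 0.07 SE. The pooled shift is about 0.001 to 0.002.

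**The case against.** The strongest reply is that the text shows a dating rule and little more, and that a reader might infer too much from it. Most of this stands:

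- **Stage 0 for every such woman.** One might infer this because level 0 is allowed. Table 3 governs the date only, Table 4 gives Stage/TNM its own assessed date, and the derivation code is in documentation not available here.
- **A subgroup known to be wrong.** Table 7 names no source variable, so the error is conditional. The subgroups are also exploratory, without formal testing.
- **All in-situ-first women wrong on every field.** Woman B is correctly not de novo and correctly above 12 months from either date. The 3 to 31 women above are therefore an upper count for the de novo error.
- **A different anchor in EDB1.** This would be an argument from silence. Models are also fitted within each database and only estimates are pooled, and section 6.1.1 discloses that curation rules vary.
- **Use in matching.** It is likely, since Table 5 marks none of the three as unavailable in EDB3. It is not confirmed, because Table 5 mixes confounders with auxiliary variables and the EDB3 balance figure is not shown.
- **The meaning of de novo.** The documents do not say whether metastatic disease after earlier in-situ disease counts as de novo.

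None of this removes the core. With the stated date rule and the stated definitions, time to index and the de novo flag follow mechanically, and the plan neither reconciles nor mentions the result. General disclosure that curation varies does not tell the analyst which date to use. Quartiles limit the leverage of an 11-year value, but Table 5 adopts them because of date imprecision, not a different starting event.

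**Conclusion.** The concern holds for in-situ-first women in EDB3. Time from diagnosis to index is counted from the in-situ lesion, and de novo status is FALSE even when the first invasive cancer was already metastatic. Stage may be 0 or may conflict with that flag. The disease-free-interval subgroup is misassigned for women metastatic at first invasive diagnosis if it is built from the same fields.

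A reader might infer that the primary result is compromised. The documents do not support that. Outcome, index date, time from metastatic diagnosis to index and the exclusion anchored on the metastatic date are untouched. The plan's power figures do not change. Bias in the hazard ratio needs an imbalance between arms, and stays within a pooled factor of about 1.024 over the assumed 0.5% to 5% and R of 1.25 to 2.0. The effect on the primary hazard ratio is expected to be very small. What is at stake is the correctness of the covariates and possibly of one exploratory subgroup. The change is worth making because it is cheap, not because the main estimate depends on it.

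**What to change.** In Table 5, define initial diagnosis as the first invasive breast cancer in every database. In EDB3, where the recorded diagnosis is in situ, re-anchor time to index, de novo status, stage and the disease-free interval to the earliest recorded invasive histology or stage I–IV assessment date. State in Table 7 which dates and flag define the disease-free interval.

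Table 4 suggests this is feasible: assessed dates are listed for "Progression, histology, lymphovascular invasion, metastatic sites, pancoast tumor, perineural invasion" and for Stage/TNM. That table serves to find the last activity for censoring, however, and does not show that an invasive date exists for each of these women. Where none is recorded, set to missing and impute only the values that cannot be determined. A known not-de-novo status should be kept; setting all three covariates to missing would discard correct information.

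Report the number of in-situ-first women by arm in EDB3, so that the assumed range above can be replaced by a count.

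The cost is a small change to the EDB3 diagnosis function, a sentence each in Tables 5 and 7, and a few extra imputed values.

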6.2. Data management

Data is stored on secure Mass General Brigham corporate provisioned and backed up servers physically located in our Mass General Brigham corporate data centers. Mass General Brigham corporate data centers are designed to insure availability of the affiliated hospitals' and research applications and IT systems in the event of a disaster. The Division follows Mass General Brigham workstation requirements which include: encryption at rest, up-to-date malware protection including antivirus, spyware detection and removal tools, CrowdStrike End Point protection installed, devices enrolled in enterprise Mobile Device Management (MDM) solution as appropriate, any laptop/computer used for business purposes must not be shared with family, friends, or other unauthorized individuals, and compliance with enterprise Password Requirements. Only authorized personnel have read-only access to raw data files.

Cleaned and analysis-ready datasets, i.e., +/- imputed one-row-per-patient tables with all required exposure, outcome and covariate variables, are stored in separate sub-directories dedicated for the specific emulated trial.

6.3. Quality control

Upon delivery, data quality procedures included checks on delivered tables and variables, per table checks, descriptives on most important measures such as demographic and stage distributions by sex at time of initial diagnosis, regimen/exposure frequency counts and time-trends and overall survival benchmarks against literature and general cancer registry statistics. The R code to reproduce the quality assessments is deposited on the Mass General Brigham-provisioned GitLab server <https://gitlab.partners.org/drugapi/encore/quality> (repository is only accessible within the Mass General Brigham network and additionally only to authorized study personnel).

6.4. Study design

[figure not shown]
Research design (e.g. cohort, case-control, etc.): Cohort study

Rationale for study design choice: Resembles the principles of the (target) trial emulation framework.

6.5. Study design diagram

Figure 1 depicts study design and variable measurement considerations for the emulation of the PALOMA-2 trial. The selection of key confounders/prognostic factors is driven by expert knowledge and additionally based on covariates included in the real-world prognostic score (ROPRO) which is a published and validated pan-tumor and cancer-specific prognostic score framework for overall survival.¹¹⁻¹⁵

Figure 1. Study design illustration for PALOMA-2 trial emulation.

- a. Proprietary business rules to define initiation of the line of therapy (including exposure assessment window) cannot be shared.
- b. De novo metastatic status, time initial diagnosis to T0, time from first evidence of metastatic disease to T0, smoking, family history, race/ethnicity, etc.
- c. Labs (albumin, hemoglobin, etc.) and vitals (BMI, etc.) that are part of the ROPRO prognostic score; see [Becker, Weberpals, et al. Ann Oncol 2020 \(doi: 10.1016/j.annonc.2020.07.013\)](https://doi.org/10.1016/j.annonc.2020.07.013)
- d. Intention-to-treat: death due to any reason or last observed clinical activity/sign of patient being alive or data cut-off date (whichever occurred earlier)

No observability criterion was applied because measures like continuous enrollment periods (claims data) are not available in electronic health records.

Abbreviations: MBC = metastatic breast cancer

6.6. Setting

6.6.1. Context and rationale for definition of time 0 (and other primary time anchors) for entry to the study population

Time 0 in this database study is defined as the date a patient initiated palbociclib plus letrozole (exposure) or letrozole alone (comparator) as part of their 1L systemic antineoplastic treatment for advanced/metastatic adenocarcinoma of the breast. This aims to emulate the date of randomization and cohort entry in the RCT (the time from randomization to first dose is not reported in the [clinicaltrials.gov study report](https://clinicaltrials.gov/study/NCT02420417) or the trial articles).

6.6.2. Context and rationale for study inclusion criteria

Study inclusion criteria were defined to emulate all key inclusion criteria for the trial that were deemed both clinically relevant and measurable in EHR data. See Excel appendix table 1 (Table1_I_E) for a one-by-one evaluation. A summary of the operational definitions of the inclusion criteria that were applied for each database can be found in the Excel appendix Table 2. In addition, the eligible time period (years) was based on the approval year of the trial's intervention drug as well as the numbers of treatment initiation. A flowchart of the study cohort assembly is provided in the appendix (10.1).

6.6.3. Context and rationale for study exclusion criteria

Study exclusion criteria were defined to emulate all key exclusion criteria for the trial that were deemed both clinically relevant and measurable in EHR data. See Excel appendix table 1 (Table1_I_E) for a one-by-one evaluation. A summary of the operational definitions of the exclusion criteria that were applied for each database can be found in the Excel appendix Table 2. A flowchart of the study cohort assembly is provided in the appendix (10.1).

6.6.4. Context and rationale for exposure(s) of interest

The exposure and comparator were defined to emulate the agents compared for the trial, i.e., initiation of palbociclib plus letrozole versus letrozole alone in a 1L metastatic setting.

- **EDB1:** Exposure is derived using a manually curated line of therapy (LOT) table provided by the data partner that programmatically categorizes treatment regimens into a coherent line of treatment, based on a proprietary business rule with an exposure assessment window. That is, each patient is represented with one row per curated line of therapy with corresponding information on line number, regimens as well start and end dates. Based on this table, patients are identified who received palbociclib-plus-letrozole or letrozole-alone treatment regimen by their generic names (string match) in 1L, using the exposure assessment window; follow-up begins after the end of the exposure assessment window. The LOT implicitly only considers regimens that were given as part of a metastatic disease setting. Importantly, the LOT table applies a proprietary business rule to determine line of therapy, which includes an exposure assessment window relative to advanced cancer diagnosis. More details and annotated code to identify initiators can be found in the 'Derive cohort EDB1' Quarto report (access within MGB network only).
- **EDB3:** Exposure is derived using a manually curated line of therapy (LOT) table provided by the data partner that programmatically categorizes treatment regimens into a coherent line of therapy, based on a proprietary business rule with an exposure assessment window. That is, each patient is represented with one row per curated line of therapy AND drug name with corresponding information online number, regimens as well start and end dates. Based on this table, patients are identified who received only palbociclib and letrozole within the first line of therapy, and letrozole alone within the first line of therapy by their generic names (string match), using the exposure assessment window; follow-up begins after the end of the exposure assessment window. The LOT implicitly only considers regimens that were given as part of a metastatic disease setting. More details and annotated code to identify initiators can be found in the 'Derive cohort EDB3' Quarto report' (access within MGB network only).
- **EDB4:** For the EDB4 database, the following logic is applied.
 - Identify patients with evidence of a metastasis from the diagnosis table in which the earliest date associated with evidence of metastasis is captured as a structured field (metastasis date).
 - Identify all potential antineoplastic drugs typically used in advanced/metastatic breast cancer (see list below*). Only these are considered.
 - Identify patients who received any of the PALOMA-2 drugs as the first antineoplastic treatment on or after the metastasis date.
 - Identify and exclude patients who received palbociclib before the metastasis date.
 - Follow-up begins after the end of the exposure assessment window.

***Antineoplastic drugs considered:** abemaciclib, alpelisib, anastrozole, atezolizumab, bevacizumab, capecitabine, carboplatin, cisplatin, cyclophosphamide, docetaxel, doxorubicin, entrectinib, epirubicin, eribulin, etoposide, everolimus, exemestane, fluorouracil, fulvestrant, gemcitabine, goserelin, ixabepilone, larotrectinib, letrozole, methotrexate, nab-paclitaxel, olaparib, paclitaxel, palbociclib, pembrolizumab, pertuzumab, ribociclib, sacituzumab govitecan-hziy, talazoparib, tamoxifen, toremifene, trastuzumab, trastuzumab-deruxtecan, vinorelbine.

